#### **14. QUALITY CONTROL AND QUALITY ASSURANCE**

During study conduct, Xeris Pharmaceuticals or its agent will conduct periodic visits to ensure that the protocol and Good Clinical Practices are being followed. The monitor may review source documents to confirm that the data recorded on CRFs is accurate. The investigator and institution will allow Xeris Pharmaceuticals' monitor or its designee, and appropriate regulatory authorities, direct access to source documents to perform this verification.

The study site may be subjected to review by the Institutional Review Board and/or to quality assurance audits performed by Xeris Pharmaceuticals or its designee, and/or to inspection by appropriate regulatory authorities. It is important that the investigator and study staff are available during the monitoring visits and possible audits or inspections and that sufficient time is devoted to the process.

## **15. DATA HANDLING, RECORD KEEPING, MONITORING AND AUDITS**

### **15.1. Case Report Forms/Electronic Data Record**

As used in this protocol, the term CRF should be understood to refer to either a paper form or an electronic data record, or both. A CRF is required and should be completed for each individual subject. The completed original CRFs are the property of Xeris Pharmaceuticals and should not be made available in any form to third parties, except for authorized representatives of Xeris Pharmaceuticals or appropriate regulatory authorities, without written permission from Xeris Pharmaceuticals.

The investigator has the responsibility for the collection and reporting of all clinical, safety and laboratory data entered on the CRFs and any other data collection forms (source documents) and ensuring that these are accurate, authentic, attributable, complete, consistent, legible, contemporaneous, enduring and available when required. The CRFs must be signed by the investigator or by an authorized staff member to attest that the data contained in the CRFs is true. Any corrections to entries made in the CRFs or source documents must be dated, initialed and explained (if necessary), and should not obscure the original entry.

In most cases, the source documents are the hospital's or physician's subject chart. In these cases, data collected on the CRFs must match the data in those charts. In some cases, the CRF, or part of the CRF, may also serve as source documents. In these cases, a document should be available at the investigator's site as well as at Xeris Pharmaceuticals and clearly identify those data that will be recorded in the CRF, and for which the CRF will stand as the source document

### **15.2. Record Retention**

To enable evaluations and/or audits from regulatory authorities or Xeris Pharmaceuticals, the investigator agrees to keep records, including the identity of all participating subjects (sufficient information to link records, e.g., CRFs and hospital records), all original signed informed consent documents, copies of all CRFs, safety reporting forms, source documents, and detailed records of treatment disposition, and adequate documentation of relevant correspondence (e.g., letters, meeting minutes, telephone calls reports). The records should be retained by the investigator according to the International Conference on Harmonisation (ICH), regulations, or as specified in the Clinical Study Agreement, whichever is longer. The investigator must obtain Xeris Pharmaceuticals' written permission before disposing of any records, even if retention requirements have been met.

### **15.3. Monitoring**

Monitoring and auditing procedures developed by Xeris Pharmaceuticals and/or its designee will be implemented to ensure compliance with FDA and ICH GCP and GLP guidelines.

The Xeris Pharmaceuticals' designated representative (the monitor or auditor) will contact the investigator and conduct regular visits to the clinical site. The monitor will be expected and allowed to verify the investigator's qualifications, to inspect clinical site facilities, and to inspect study records, including proof of IRB review, with the stipulation that subject confidentiality will

be maintained in accordance with local and federal regulations, including HIPAA requirements. The monitor will also be responsible for confirming adherence to the study protocol, inspecting CRFs and source documents, and ensuring the integrity of the data. CRFs will be checked for accuracy, completeness, and clarity and will be cross-checked for consistency with source documents, including laboratory test reports and other subject records. Instances of missing or uninterpretable data will be resolved in coordination with the investigator.

The monitor/auditor will also investigate any questions concerning adherence to regulatory requirements. Any administrative concerns will be clarified and followed. The monitor will maintain contact with the site through frequent direct communications with the study site by e-mail, telephone, facsimile, and mail. The investigator and all other site personnel agree to cooperate fully with the monitor and will work in good faith with the monitor to resolve any and all questions raised and difficulties detected by the monitor.

#### **15.4. Audits and Inspections**

The investigator understands that regulatory authorities, the IRB, and/or Xeris Pharmaceuticals or their designees have the right to access all CRFs, source documents, and other study documentation for on-site audit or inspection and will retain this right from the start of the study to at least 2 years after the last approval of a marketing application or for at least 2 years after clinical development of the study drug for the indication being studied has been discontinued. The investigator is required to guarantee access to these documents and to cooperate with and support such audits and inspections.

## **16. ETHICAL CONSIDERATIONS**

### **16.1. Conduct**

This protocol is written in accordance with the principles established by the 18th World Medical Assembly General Assembly (Helsinki, 1964) and amendments and clarifications adopted by the 29th (Tokyo, 1975), 35th (Venice, 1983), 41st (Hong Kong, 1989), 48th (Somerset West, South Africa, 1996), 52nd (Edinburgh, 2000), 53rd (Washington, 2002), 55th (Tokyo, 2004), and 59th (Seoul, 2008) General Assemblies. The investigator will ensure that the study described in this protocol is conducted in full conformance with those principles, the protocol, current FDA regulations, ICH Good Clinical Practices (GCP) guidelines, Good Laboratory Practices (GLP) guidelines, local ethical and regulatory requirements, including the Federal Food, Drug and Cosmetic Act, U.S. applicable Code of Federal Regulations (title 21), any IRB/IEC requirements relative to clinical studies.

Should a conflict arise, the investigator will follow whichever law or guideline affords the greater protection to the individual subject. The investigator will also ensure thorough familiarity with the appropriate administration and potential risks of administration of the study drug, as described in this protocol and the Investigator's Brochure, prior to the initiation of the study.

### **16.2. Institutional Review Board (IRB)**

The Ethics Committee/IRB must be a properly constituted board or committee operating in accordance with 21 CFR Part 56, "Institutional Review Boards." This protocol, any protocol amendments, the associated informed consent forms, and the informed consent procedures must be submitted to the IRB for review and approved before the enrollment of any subject into the trial. Study drug may not be shipped to the investigator until Xeris Pharmaceuticals has received a copy of the letter or certificate of approval from the IRB for the protocol and any protocol amendments.

All types of subject recruitment or advertising information must be submitted to Xeris Pharmaceuticals or its designee and to the IRB for review and approval prior to implementation. IRB approval of any protocol amendments must be received before any of the changes outlined in the amendments are put into effect, except when the amendment has been enacted to eliminate a potential hazard to study subjects. In such cases, the chair of the IRB should be notified immediately and the amendment forwarded to the IRB for review and approval.

It is the responsibility of the investigator to have prospective approval of the study protocol, protocol amendments, informed consent documents, and other relevant documents, e.g., recruitment advertisements from the IRB. All correspondence with the IRB should be retained in the Investigator File. Copies of IRB approvals should be forwarded to Xeris Pharmaceuticals.

### **16.3. Subject Information and Consent**

All parties will ensure protection of subject personal data and will not include subject names on any sponsor forms, reports, publications, or in any other disclosures. Subject names, address, date of birth and other identifiable data will be replaced by a numerical code consisting of a numbering system provided by Xeris Pharmaceuticals to de-identify the study subject. In the

case of data transfer, Xeris Pharmaceuticals will maintain confidentiality and protection of subject personal data.

The informed consent document used in this study, and any changes made during the course of the study, must be prospectively approved by both the IRB and Xeris Pharmaceuticals before use. The investigator must ensure that each study subject is fully informed about the nature and objectives of the study and possible risks associated with participation. The investigator, or a study staff designated by the investigator, will obtain written informed consent from each subject before any study-specific activity is performed. The investigator will retain the original of each subject's signed consent document. Receipt of written informed consent will be documented in each subject's or potential subject's CRF. The signed informed consent document must remain on file at the study site and be available for verification by the study monitors at all times.

#### **16.4. Subject Recruitment**

All types of subject recruitment or advertising information must be submitted to Xeris Pharmaceuticals or its designee and to the IRB for review and approval prior to implementation. Advertisements approved by the IRB may be used as recruitment procedures.

#### **16.5. Reporting of Safety Issues and Serious Breaches of the Protocol**

In the event of any prohibition or restriction imposed (i.e., clinical hold), or if the investigator is aware of any new information which might influence the evaluation of the benefits and risks of the investigational product, Xeris Pharmaceuticals should be notified immediately. In addition, the investigator will inform Xeris Pharmaceuticals immediately of any urgent safety measures taken by the investigator to protect study subjects against any immediate hazard, and of any serious breaches of this protocol.

## **17. DEFINITION OF END OF TRIAL**

LSLV for each site is defined as the date the last subject completes the follow-up visit (Visit 4), with the understanding that final review by the investigator may be delayed a few days to allow for receipt of final lab results.

## **18. PROCEDURES FOR MODIFYING THE PROTOCOL OR TERMINATING THE STUDY**

### **18.1. Protocol Modifications and Deviations**

The principal investigator must sign this protocol and its amendments (if any) before initiating the study at a particular site. The investigator will make all reasonable efforts to comply with the written protocol. Protocol modifications to ongoing studies that affect the safety of subjects or that alter the scope of the investigation, the scientific quality of the study, the experimental design, dosing, study assessments, the number of subjects exposed to test drug, or subject selection criteria must be made only after consultation between Xeris Pharmaceuticals and the investigator. All protocol modifications must be reviewed and approved by the IRB before the revised protocol can be implemented. Emergency revisions that eliminate an apparent hazard to subjects do not require preapproval by the IRB. However, the IRB must be notified in writing as soon as possible after the modification has been made. A copy of this communication must be forwarded to Xeris Pharmaceuticals. All departures from the protocol must be fully documented in the source documents and the CRFs of the subjects involved.

### **18.2. Study Termination**

The study may be prematurely terminated at any time because of a regulatory authority decision, change in opinion of the IRB, safety problems, or at the discretion of Xeris Pharmaceuticals or the principal investigator. Circumstances that may warrant premature study termination include, but are not limited, to the following:

- Determination of unexpected, significant, or unacceptable risk to subjects,
- Failure to enter subjects at an acceptable rate,
- Insufficient adherence to the requirements of the protocol,
- Insufficient provision of complete and evaluable data, or
- Plans to modify, suspend, or discontinue development of the study drug.

If the study is prematurely terminated or discontinued, Xeris Pharmaceuticals will promptly notify the investigator documenting the reason for study termination, and specific procedures for termination will be arranged by the sponsor in coordination with the investigator. After notification, the investigator must contact all participating subjects within 7 days. All study materials must be collected and all CRFs completed to the greatest extent possible, and all study materials must be returned to Xeris Pharmaceuticals or its designee within an additional 28 days.

## **19. PUBLICATION OF STUDY RESULTS**

Publication of study results is discussed in the Clinical Study Agreement.

## APPENDICES

### APPENDIX 1. HYPOGLYCEMIA SYMPTOM QUESTIONNAIRE

*Investigative Site Instructions:* The subject should complete the Hypoglycemia Symptom Questionnaire at the following time points:

- Just before the IV bolus push dose of insulin is given at the start of the hypoglycemia induction procedure.
- Every time blood is drawn for evaluation of plasma glucose concentration during the induction procedure.
- Just before study drug is administered.
- Every 5±2 minutes after glucagon is administered, until all symptoms have abated (i.e., all symptoms have score = 1) or 45 minutes post-dosing, whichever occurs first.

*Note:* If a subject is unable to physically complete the questionnaire, the subject will provide verbal responses, which will be recorded on the questionnaire by study staff. Documentation will be provided on each completed questionnaire as to who completed the form.

*Subject Instructions:* Please rate the current intensity (severity) of each of the following symptoms on a scale of 1-6, with a minimum score of “1” meaning the symptom was absent and a maximum score of “6” meaning the symptom was severe. For the final question, please answer “yes” or “no.”

Neuroglycopenic Symptoms	Severity Score (1-6)
Dizziness	
Blurred vision	
Difficulty in thinking	
Faintness	
Autonomic Symptoms	Severity Score (1-6)
Sweating	
Tremor	
Palpitations	
Feeling of nervousness	
Overall Assessment of Hypoglycemia	Yes/No
Do you currently feel hypoglycemic?	

## APPENDIX 2. INJECTION SITE DISCOMFORT ASSESSMENT

### Visual Analog Scale (VAS) for Injection Site Discomfort

*Investigative Site Instructions:* The subject should complete the 100-mm Visual Analog Scale (VAS) for Injection Site Discomfort at both **10±5** minutes and **30±5** minutes following the injection of study drug, and again before the end of the clinic visit (i.e., at 240±5 minutes post-dosing) if the VAS score at **30±5** minutes is > 0 mm. The subject completes the VAS by drawing a single vertical line through the scale corresponding to the perceived intensity (severity) of discomfort according to the instructions below. The goal is for the subject to report the amount of discomfort, if any, remaining at each time point, as opposed to reporting the transient pain associated with needle insertion.

[figure not shown]
*Note:* If a subject is unable to physically complete the questionnaire, the subject will indicate the point on the VAS corresponding to their level of discomfort, and study staff will enter a vertical line at that point. Documentation will be provided on each completed questionnaire as to who completed the form.

**Please verify the length of the VAS line to be 100-mm before providing it to the subject.**

*Subject Instructions:* Ignoring any pain from insertion of the needle, please draw a single vertical line through the scale below that corresponds to the intensity (severity) of any discomfort you are feeling **right now** at the study drug injection site.

Discomfort could include stinging, burning, tingling, throbbing or pain. The further to the right you make your vertical mark, indicates the more intense discomfort you are feeling.

You should normally draw a straight line across the scale to indicate your current level of discomfort. However if you are currently feeling no discomfort, you should circle the vertical line on the left end of scale (above the word “no”). If you are currently feeling the worst discomfort possible, you should circle the vertical line on the right end of the scale.

**Injection Site Discomfort Description and Duration Questionnaire**

*Study Personnel Instructions:* Question 1a should be should be completed by the subject at **10±5** minutes following the injection of study drug. Any subject reporting discomfort other than “none,” should complete question 1b. Any subject reporting a duration of discomfort of “at least 10 minutes” should complete follow-up question 1c at the end of the study visit. The goal is for the subject to report the qualitative nature and duration of discomfort, if any, associated with injection of study drug, ignoring any transient pain associated with needle insertion.

*Note:* If a subject is unable to physically complete the questionnaire, the subject will provide verbal responses, which will be recorded on the questionnaire by study staff. Documentation will be provided on each completed questionnaire as to who completed the form.

*Subject Instructions:* Please answer question 1a and, if applicable to you, questions 1b and 1c. In answering these questions, you should ignore any pain from insertion of the needle.

1a. How would you describe any discomfort you felt from the study drug? (Check **all** that apply):

- None (**Please ignore question 1b.**)
- Pain (e.g., throbbing, soreness, muscle ache)
- Itching
- Tingling, twitching or numbness
- Irritation (e.g., burning, stinging)

Other or additional comments: \_\_\_\_\_

1b. About how long did the discomfort last after the injection? (Check one):

- Less than 1 minute
- 1-2 minutes
- 3-5 minutes
- 6-9 minutes
- at least 10 minutes (**Please complete question 1c before leaving the clinic.**)

1c. In total, how long did the discomfort last after the injection? (Please enter a number below):

\_\_\_\_\_ Minutes

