  - d. Every 5±2 minutes after glucagon is administered until all symptoms have abated (i.e., all symptoms have score = 1) or 45 minutes post-dosing, whichever occurs first.
9. Local tolerability will be assessed as follows:
  - a. Subjects will complete a Visual Analog (VAS) questionnaire regarding injection site discomfort ([Appendix 2](#)) at 10±5 and 30±5 minutes post-dosing, and again at 240±5 minutes post-dosing if VAS score reported at 30 minutes is > 0 mm.
  - b. Subjects will complete an Injection Site Discomfort Description and Duration Questionnaire at 10±5 minutes post-dosing. If discomfort is ongoing at 10 minutes post-dosing, the questionnaire will be updated before the subject leaves the clinic to document the final duration.
  - c. An investigator will use the modified Draize scales ([Appendix 3](#)) to assess erythema and edema formation at the injection site at 10±5 and 30±5 minutes following administration. Any injection site with a score > 0 for either erythema or edema at 30 minutes post-dosing will be re-evaluated for both at 240±5 minutes post-dosing. If any scores remain > 1 at the 240-minute evaluation, the subject may leave the clinic but will be instructed to contact study staff if the condition fails to resolve.
10. Adverse events reported by the subject or observed by an investigator will be recorded in the CRF.

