#### **13.3.6. Local Tolerability:**

The incidence of any injection site discomfort (score >0 on the ordinal rating scale) will be analyzed descriptively. The incidences of erythema and edema will be analyzed in a similar manner. Descriptive statistics (only) will be provided for time of onset and duration (of discomfort) and discomfort description (i.e., pain, irritation, itching, etc.). Mean VAS scores will be compared between the treatments.

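### The Appendix 2 form opens the discomfort-duration follow-up on a different condition from Section 10.2.1 item 9b, so continuing discomfort can be recorded as a short episode; the time of onset that Section 13.3.6 will summarise is not asked

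*Combined protocol and SAP*

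**What the plan says.** Section 10.2.1 item 9b sets the timing: "Subjects will complete an Injection Site Discomfort Description and Duration Questionnaire at 10±5 minutes post-dosing". It then gives an update rule: "If discomfort is ongoing at 10 minutes post-dosing, the questionnaire will be updated before the subject leaves the clinic to document the final duration". Section 10.2.2 repeats these procedures at the second treatment visit.

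Appendix 2 reproduces the form. Question 1a asks the type of discomfort, and its instruction places it at 10±5 minutes. Question 1b asks "About how long did the discomfort last after the injection", with five bands: under 1 minute, 1-2, 3-5, 6-9, and ten minutes or more. Only a subject who chooses the last band "should complete follow-up question 1c at the end of the study visit". Question 1c asks "In total, how long did the discomfort last after the injection" and takes a number of minutes.

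Section 13.3.6 states the analysis: "Descriptive statistics (only) will be provided for time of onset and duration (of discomfort)". Mean VAS scores are to be compared between the treatments.

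**The concern.** The protocol body and the form have the same purpose, to obtain the final duration when discomfort outlasts the questionnaire, but they open the follow-up on different conditions. Item 9b looks at whether discomfort is present at 10 minutes. The form looks at whether the subject has already reported ten minutes of it. These agree only if the form is completed at or after 10 minutes, and the window permits earlier completion.

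Where they disagree, the error runs one way: a continuing episode is stored as a finished, shorter one. It therefore removes most from whichever product has the longer-lasting discomfort. The documents do not say which that is, but the products differ in vehicle and volume (Section 9.3: 0.2 mL of non-aqueous DMSO solution against a vial reconstituted with 1 mL of diluent). Comparing tolerability is a secondary objective (Section 5.2), and subject-reported discomfort is a listed secondary endpoint (Section 5.3.2). Under Section 12.2, injection site reactions are not adverse events unless they need medical intervention, so adverse-event data will usually not supply a duration that the form has missed.

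The second gap is simpler. A summary of time of onset is planned, and none of the discomfort instruments shown asks for it.

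**Working it through.** The documents state no figure on this point to reproduce. The check is window arithmetic and a comparison of the texts.

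**Inputs**
- Questionnaire window: 10±5 minutes (Section 10.2.1 item 9b).
- Bands in 1b and the condition for 1c (Appendix 2).
- Update condition: ongoing at 10 minutes (item 9b).
- VAS: 10±5 and 30±5 minutes, and 240±5 minutes if the 30-minute score is above 0 (item 9a, Appendix 2).

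**Step 1: the window.** 10 − 5 = 5 and 10 + 5 = 15, so completion from 5 to 15 minutes after dosing is compliant.

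**Step 2: a subject whose discomfort is still present when the form is completed**

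| Completed at | Longest band already reached | 1c opened by the form? | Update required by item 9b? |
|---|---|---|---|
| 5 min | 3-5 min | No | Yes, if still present at 10 min |
| 6 to 9 min | 6-9 min | No | Yes, if still present at 10 min |
| 10 to 15 min | 10 min or more | Yes | Yes |

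The rules part company in the first two rows. The subject has not yet had ten minutes of discomfort, so cannot accurately choose the band that opens 1c, and has no way to record that it continues.

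**Step 3: is there a fixed check at 10 minutes?** The first VAS and the first Draize assessment also carry 10±5 windows. All three can be done at 5 or 6 minutes, and no further discomfort question is then scheduled until the 30±5 minute VAS.

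**Step 4: can the VAS recover the duration?** It measures intensity at the moment of asking. The second reading falls no earlier than 30 − 5 = 25 minutes. If discomfort ends after minute 10 but before that reading, an early form shows a band of 9 minutes or less and the second VAS is zero, so nothing looks wrong. If discomfort is still present at the second reading, the VAS contradicts the short band but does not give the duration. The documents contain no rule for reconciling the two.

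**Step 5: onset.** Question 1a gives type, 1b banded duration, 1c total minutes, and the VAS current intensity. None gives the time from injection to first discomfort.

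**Step 6: how many subjects?** The part of the window before 10 minutes is 10 − 5 = 5 of its 15 − 5 = 10 minutes. That is a share of permitted time, not of forms. The documents give no completion times, so the share of early forms could lie anywhere from 0% to 100%. The subjects affected are a subset: form early, discomfort still present at 10 minutes, and item 9b's update not made.

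**The case against.** The strongest reply is that item 9b already covers the case. Its update does not depend on the band chosen, so a site that follows the protocol body will go back to a subject who answered at minute 7 and still has discomfort at minute 10. This stands. A reader might infer that such records are never updated; the documents do not support that. What remains is that the form's own instruction gives no route to 1c from a shorter band, so staff must override it to comply with item 9b.

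A reader might also infer that nobody is present to notice discomfort at 10 minutes. That is not supported either. Glucose is drawn and, while symptoms last, the hypoglycemia symptom questionnaire is completed every 5±2 minutes, so staff contact falls at about 8 to 12 minutes. The hypoglycemia questionnaire does not ask about the injection site, however, so contact alone does not prompt the update.

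Appendix 2 times only question 1a at 10±5 minutes and gives 1b no clock time. That is correct, but item 9b times the whole questionnaire, so answering 1b early is compliant.

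Duration is not the only within-subject measure of local tolerability. VAS, type of discomfort, erythema and edema are also collected at both treatment visits, and mean VAS is compared between treatments. This limits how much rests on duration.

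On onset, Section 13.5 leaves analysis detail to the SAP. An analysis plan can define a summary, but it cannot supply times that were not collected.

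**Conclusion.** The point holds as a minor inconsistency with two parts. First, the form's condition for 1c conflicts with item 9b, and an early form can leave continuing discomfort in a band of 9 minutes or less. The error can only shorten durations. Second, the planned onset summary has no visible data source.

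The number of subjects affected cannot be computed. A reader might take half of the forms to be early because half of the window lies before 10 minutes. That would require completion times spread evenly over 5 to 15 minutes, which nothing in the documents supports, and it would count forms rather than subjects with a lost duration. Nor can it be said that either product will look better tolerated than it is, since the documents do not say whose discomfort lasts longer.

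The consequence is limited to descriptive local-tolerability output. The primary analysis and the sample size do not use these items. The conclusion assumes that the form in use is the one shown in Appendix 2 and that no case report form page outside the documents asks for onset.

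**What to change.** 1. Make the form match item 9b in one of two ways. Either add a still-ongoing answer to question 1b and let it, as well as the ten-minutes-or-more band, open 1c; or bar completion before 10 minutes by setting the window to 10 minutes −0/+5 in item 9b and in Appendix 2, stating that it covers 1b as well as 1a. Either closes the gap. The first keeps the present window, and its only side effect is that some subjects whose discomfort stops before 10 minutes also answer 1c.
2. Allow ongoing at discharge as an answer to 1c, and report those subjects as a separate count in the duration summary.
3. Add one item asking the minutes from injection to first discomfort, or delete time of onset from Section 13.3.6.

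The cost is a form edit and, depending on the options chosen, a changed window or one sentence in Section 13.3.6. No visit or procedure is added. The change should be made before dosing starts, because missed durations and onset times cannot be reliably recovered afterwards.
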